6.12.2. Adverse Events

An **adverse event (AE)** is an event occurring after informed consent; or an event that is the same as a preexisting condition but has increased in severity/seriousness/relatedness after informed consent was signed; or a historical condition that recurs after the informed consent has been signed.

Preexisting conditions and AEs will be entered on the CRFs as follows. If a preexisting condition has not resolved at the time of study entry, and there are changes in severity, becomes serious without a change in severity, or the condition is considered related to study treatment or

procedures by the investigator, the event is classified as an AE and a new record with a new start date is entered in the AE CRF. If a condition that had already ended recurs after the informed consent has been signed, then the recurrence is classified as an AE and is entered with the new start date in the AE CRF. Any other events that occur after the informed consent is signed are entered in the AE CRF. If the AE has not resolved but there is a change in severity (or there is a change in seriousness not related to severity), then the date of the change is entered as the end date and a new AE record is generated. The start date of the new AE will be the date of the new status and will be equal to the end date of the previous status.

AEs will be coded using the Common Terminology Criteria for Adverse Events (CTCAE) v 4.0 or higher and MedDRA (MedDRA Version 16.0 or higher) and two hierarchies will be in SDTM. The MedDRA hierarchy will be created centrally by mapping the verbatim reported term to a MedDRA lower level term (LLT) and preferred term (PT) and, for the second hierarchy, the mapping will be from the investigator reported CTCAE term (except in the case “other-specify” within an SOC where the LLT will be obtained from the centrally mapped term, but will also be stored in a variable prefixed by CTC). All AE summaries will use the mappings to LLT, PT and SOC from the investigator reported CTCAE. Only variables prefixed by CTC in the AE or AE suppqual SDTM domains will be used in reporting.

A treatment emergent AE (TEAE) is any AE initially occurring after 1st dose; or if initially occurring pre-dose and ongoing at time of first dose (may be a pre-existing condition or AE) and severity of the reoccurrence is greater than the max severity pre-dose; then the reoccurrence is a TEAE. The time frame post-dose includes end of short term follow up period. The CTC LLT will be used to compare pre-dose and post-dose events in the TEAE algorithm.

1. Compare the post-dose LLT with LLT of preexisting conditions/AEs ongoing at first dose:
 - a. If the post-dose LLT is not present as a pre-dose term, then the AE is a TEAE
 - b. If the LLT is present as a pre-dose term AND the severity increases post-dose compared with the most severe pre-dose grade for the same LLT, then the event is a TEAE
2. Time frame post-dose includes end of short term follow up period – that is, 30 days post discontinuation of study treatment.

Treatment-emergent AEs excludes any AE which maps to a LLT recorded at baseline and has the same or lower severity as that at baseline, even if considered drug related or serious.

Treatment-related AEs are events considered as having at least a suspected relationship to the study drug as entered on the CRF.

If the severity grade or relationship to the study drug of an AE is missing, a worst-case scenario will be assumed (that is, Grade 4 or related for post-dose AEs, and Grade 1 or not related for pre-dose AEs).

Specifically, the following summary tables will be provided:

- An overview of AEs including the number and percentage of patients with ≥ 1 TEAE, ≥ 1 CTCAE Grade 3/4, ≥ 1 SAE, who discontinued study treatment due to AE, discontinued study treatment due to SAE, died due to AE on study treatment, and died due to AE within 30 days of discontinuation from study treatment. Additionally, the number of AEs related to study treatment in each of the previous categories will be given.
- The number and percentage of patients experiencing the following TEAEs by treatment group, SOC and PT:
 - TEAEs
 - Related and regardless of relatedness to study drug
 - TEAEs leading to discontinuation from study treatment
 - TEAEs leading to discontinuation from study treatment by serious criteria
 - Related and regardless of relatedness to study drug
 - SAEs
 - TEAEs by maximum reported CTCAE grade
 - Related and regardless of relatedness to study drug
 - TEAEs grouped by maximum CTCAE grade (Any grade, Grades 1/2, Grades 3/4/5, Grade 5)
 - Related and regardless of relatedness to study drug
- The number and percentage of patients experiencing the following TEAEs by treatment group and PT:
 - TEAEs leading to death (also see Section [6.12.4](#))
- The number and percentage of patients experiencing laboratory CTCAEs
 - Maximum derived CTCAE grade by cycle/visit
 - Shift from baseline to worst CTCAE grade post baseline by laboratory parameter

In the tabulations a patient with multiple adverse events within a SOC or PT is only counted once towards the total of this SOC or PT.

All AEs will be listed by treatment group, patient and onset date. Additionally, a separate listing will subset all SAEs. The definition of TEAE allows for the possibility of a treatment-related AE that is not classified as treatment emergent (for example, a treatment related AE that occurs after treatment has started that is the same severity as the same AE that occurred prior to treatment). Any AEs fitting this category will be listed.

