In the East Asia (China, Taiwan, and South Korea) ASIAN-Pacific trial, which compared sorafenib with placebo in patients with advanced liver cancer with no prior systemic treatment, median OS was 6.5 months (95% CI: 5.56, 7.56) in patients treated with sorafenib, compared with 4.2 months (95% CI: 3.75, 5.46) in those who received placebo (HR: 0.68 [0.50–0.93];  $p=.014$ ). Median TTP was 2.8 months (95% CI: 2.63, 3.58) in the sorafenib group compared with 1.4 months (95% CI: 1.35–1.55) in the placebo group (HR: 0.57 [0.42–0.79];  $p=.0005$ ). The most frequently reported grade 3/4 drug-related adverse events (AEs) in the 149 assessable patients treated with sorafenib were hand-foot skin reaction (16 patients [10.7%]), diarrhea (9 patients [6.0%]), and fatigue (5 patients [3.4%]) (Cheng et al. 2009).

Given these results, sorafenib is the first-line standard of care for patients with advanced liver cancer who are not candidates for surgical or local treatment. However, if the treatment with

sorafenib failed, there is no approved second-line therapy. Available results of sorafenib in the Asian population are summarized in [Table JBAS.5.1](#).

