- If the patient, for any reason, requires treatment with another therapeutic agent that has been demonstrated to be effective for treatment of the study indication, discontinuation from the study drug(s) occurs prior to introduction of the new agent.
- patient decision
  - the patient requests to be withdrawn from the study or study drug.
- sponsor decision
  - Lilly stops the study or stops the patient's participation in the study for medical, safety, regulatory, or other reasons consistent with applicable laws, regulations, and good clinical practice (GCP).
- patient is significantly noncompliant with study procedures and/or treatment.
- unacceptable toxicity: patients who discontinue sorafenib because of toxicity may continue LY2157299 or placebo treatment.
- patient becomes pregnant or fails to use adequate birth control (for women with reproductive potential)

The reason for and date of discontinuation will be collected for all patients. All randomly assigned patients who discontinue regardless of whether or not they received study drug, will have procedures performed as shown in the Study Schedule ([Attachment 1](#)).

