**Figure JBAS.8.2. JBAS extension period design.**

## 8.2. Discussion of Design and Control

Approximately 150 patients will be entered in order to randomly assign 120 patients to 1 of 3 treatment arms using a 1:2:1 allocation ratio in favor of the LY2157299 plus sorafenib arm. A randomized, controlled design is being used in this study. Randomization minimizes systematic

bias in the selection and assignment of patients to study therapy and provides justification for inferential statistical methods to be used on data from this study. The study will use a dynamic allocation method, introduced by Pocock and Simon (1975) (and extended for unequal treatment group sizes by Han et al. [2009]) to minimize imbalance between treatment arms according to factors such as AFP and portal vein thrombosis. Using an appropriate concurrent control arm (which is sorafenib in combination with placebo) enables direct statistical estimation of benefits and harms due to study therapy and minimizes bias in the assessment and interpretation of observed treatment effects. The rationale behind favoring the combination arm in the randomization is that this is the primary treatment of interest to compare with sorafenib alone. However, based on the longer time to progression observed in Study JBAK patients in whom LY2157299 was administered as a monotherapy in a first-line setting, there is medical need of getting more information for efficacy and safety of LY2157299 monotherapy. Therefore, a monotherapy arm is also included and will inform future Phase 3 development. The purpose of the monotherapy arm is to provide a comparison to assess the safety of LY2157299 compared to sorafenib. This is especially important because LY2157299 has shown preclinical cardiac toxicity, which, thus far, has not confirmed in clinical studies. However, sorafenib has known cardiac toxicity in patients. The 3-arm study will provide a better differentiation between the various safety profiles and inform the design of Phase 3. Since OS is not affected by pseudoprogression evaluations, OS is a preferred primary endpoint over TTP or PFS. A Bayesian design can be used to leverage survival data for sorafenib alone from historical clinical trials to benefit from the 2:1 randomization of the combination arm relative to sorafenib alone with the goal of increasing power over an otherwise similar design.

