### 10.1. Efficacy Measures

All patients will be followed for progression and OS. Patients who come off therapy due to objective progressive disease will be followed for survival every 2 months. Patients may continue on study treatment even if they have objective progression or if they are clinically asymptomatic (see Section 7.3). However, it is important that the cycle response records

objective progressive disease in the cycle that it occurred in order to estimate TTP, PFS, and response rate without bias. These patients will then be discontinued from study treatment because of overall symptomatic deterioration (including biomarker response) or other causes. Patients who come off therapy and do not have objective progressive disease should be followed every 2 months after discontinuation from study treatment until death, including radiologic examinations every 6 weeks until objective progressive disease is determined (using the same radiological scans as at baseline). Patients who progress should then be followed for survival every 2 months. Every attempt should be made to gather all information every 2 months (radiological scans and survival), even if a patient starts a new anticancer therapy. Evaluation of survival can be accomplished by telephone contact if necessary. The date any new anticancer therapy starts, either during the 30-day safety or long-term follow-up periods, needs to be collected. This will enable a better estimate of time-to-event data to inform future decisions in this indication as it will be based on more mature data.

It is important that protocol procedures related to collection of these data, both during the active study treatment phase and follow-up period, are followed and that dates of data collection are recorded accurately.

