- i If the patient has clinically significant cardiac findings at discontinuation (Visit 801), echocardiography with Doppler and ECG and ECG chemistry will be repeated every 2 months for 6 months (Visits 803, 804, and V805). If there are no cardiac findings at discontinuation (Visit 801), 1 more echocardiography with Doppler, ECG, and ECG chemistry will be performed after 2 months (Visit 802) unless a patient is receiving another treatment (see Section [10.3.2.2](#)).
- j If there were no clinically significant findings at the last assessment conducted within the 30 days following discontinuation and the patient has started another treatment, Visit 801 CT scan or chest MRI with contrast will not be performed.
- k Repeat radiological scans at study discontinuation may be omitted if a patient has objective disease progression or if imaging has been performed in the previous 3 to 6 weeks.
- l Within 60 days prior to randomization; includes HBsAg, hepatitis B surface antibody, total hepatitis B core antibody, hepatitis B e antigen, hepatitis B e antibody, hepatitis B virus DNA, hepatitis C RNA.
- m HBsAg carriers should be closely monitored with assessment of hepatitis B serology during the study treatment and 30-day safety follow-up period.
- n  $\pm$ 3 days after end of treatment with LY2157299.

Study Schedule, Protocol H9H-MC-JBAS: Extension Period

Cycle (Visit)	Study Treatment (v501, v502, etc) a	Post Discontinuation Follow-Up Periods		Comments
		30-day Safety Follow-Up (v801)	Long-Term Follow-Up b (v802)	
Refer to Section 10 of the protocol for descriptions of the study periods				
Procedures				
Physical exam	X	X		Performed once per cycle on Day 1 of each cycle in extension period
Vital signs (heart rate, blood pressure, weight)	X	X		Performed once per cycle predose on Day 1 of each cycle in extension period
CTCAE grading	X	X	X c	Performed once per cycle predose on Day 1 of each cycle in extension period
Concomitant medications	X	X	X	Performed once per cycle predose on Day 1 of each cycle in extension period
Performance status	X	X		Performed once per cycle predose on Day 1 of each cycle in extension period
Imaging procedures				
Echocardiography with Doppler d	X	X e	X e	For patients receiving galunisertib: Performed once per cycle predose on Day 1 of every other cycle in the extension period.

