6.1.1. Analysis Populations

The following populations used for analysis are defined in [Table JBAS.6.2](#) below.

Table JBAS.6.2. Populations used for Analysis

Population	Definitions or Rule
Randomized	Patients who have been randomized to study treatment. Patients in this set will be grouped according to their allocated treatment. All subject characteristics and efficacy analyses (except tumor response) will be conducted on this population.
Per-protocol	Patients who have been randomized to study treatment and did not have any major protocol deviations. Patients in this set will be grouped according to their allocated treatment. Efficacy analyses might be conducted on this population in addition to the randomized population.
Tumor response qualified	Patients who have been randomized to study treatment, received at least 1 dose of study treatment (LY2157299, LY2157299-matched placebo, or sorafenib), had measurable disease at baseline and had at least one baseline and one study treatment period tumor assessment. Tumor response analyses (Section 6.9.2.2) will be conducted on this population. Patients in this set will be grouped according to their allocated treatment, and then the analysis will be repeated using the actual treatment assignment.
Safety	Patients who have been randomized to study treatment and have received at least 1 dose of study treatment (LY2157299, LY2157299-matched placebo, or sorafenib). Patients will be grouped according to actual treatment received in Cycle 1. Safety analyses and efficacy analyses as specified in Section 6.9.2.1 will be performed on this population.

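### The 30-day treatment-emergent window has no cut at the next anticancer therapy, so the all-causality safety tables can count post-study sorafenib toxicity, probably mainly in the LY2157299 monotherapy arm

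*SAP*

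**What the plan says.** SAP 6.12.2 sets the window twice, in the definition ("The time frame post-dose includes end of short term follow up period") and again in the algorithm ("Time frame post-dose includes end of short term follow up period – that is, 30 days post discontinuation of study treatment"). No other end point is given. SAP 6.1.1 fixes the arm in the safety tables: "Patients will be grouped according to actual treatment received in Cycle 1". An event that begins after a later switch of drug therefore stays with the Cycle 1 arm.

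The protocol foresees a switch inside that window. Section 10.1 says: "The date any new anticancer therapy starts, either during the 30-day safety or long-term follow-up periods, needs to be collected". A footnote to the study schedule in Attachment 1 covers a patient with no clinically significant findings at the last assessment in the 30 days after discontinuation: if "the patient has started another treatment, Visit 801 CT scan or chest MRI with contrast will not be performed". Section 7.3.1 requires only that "discontinuation from the study drug(s) occurs prior to introduction of the new agent"; it sets no interval.

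Protocol Section 5 describes sorafenib as the first-line standard of care and says that if treatment with "sorafenib failed, there is no approved second-line therapy". Patients with previous systemic treatment for advanced disease are excluded (Section 7.2). On the monotherapy arm, Section 8.2 says: "The purpose of the monotherapy arm is to provide a comparison to assess the safety of LY2157299 compared to sorafenib". Section 12.2.11 plans to compare adverse event incidence between arms with Fisher's exact test. SAP 6.6.3 lists and counts post-discontinuation therapies but does not link them to the TEAE algorithm.

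**The concern.** A patient who stops LY2157299 monotherapy and starts sorafenib a week later still has about three weeks in which every new event is counted under LY2157299. Such a patient has not yet had the standard drug, so sorafenib is the plausible next step. A patient leaving Arm 2 or Arm 3 has already had it, and the protocol names no approved successor. The carry-over would therefore be unequal between arms.

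The events at stake are the ones meant to separate the drugs: hand-foot skin reaction, diarrhea and cardiac events. Section 8.2 says that sorafenib has known cardiac toxicity in patients, while that of LY2157299 has so far been seen only preclinically. Sorafenib events counted in Arm 1 pull the Arm 1 versus Arm 3 comparison toward no difference and could be read as toxicity of LY2157299.

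**Working it through.** **1. How the plan treats the next therapy elsewhere.** SAP 6.9 counts TTP and PFS events only before post-discontinuation anticancer therapy and censors there. SAP 6.12.7 drops the Visit 802 cardiac assessments once another treatment starts. The TEAE definition has no matching rule. Protocol 5.1.3 says LY2157299 is fully eliminated after 14 days off drug, so about half of the 30-day window lies beyond elimination.

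**2. Share of the window after discontinuation.** As a proxy for time on drug, take the median TTP in the earlier HCC study (Protocol 5.1.5.1): 12.0 weeks overall and 18.3 weeks in 20 sorafenib-naive patients. With exponential times, the mean is median/ln 2, and 30 days is 4.29 weeks.

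- 12.0/0.693 = 17.3 weeks; 4.29/(17.3 + 4.29) = 20%.
- 18.3/0.693 = 26.4 weeks; 4.29/(26.4 + 4.29) = 14%.

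Treating the medians as fixed durations gives 26% and 19%. Treatment may continue past objective progression (Protocol 10.1), which would make the share smaller.

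**3. Inputs that reproduce.** Arm 1 and Arm 3: 120 x 1/4 = 30 each. Drug-related Grade 3/4 rates in the placebo-controlled East Asian sorafenib trial (Protocol 5): 16/149 = 10.7% hand-foot skin reaction, 9/149 = 6.0% diarrhea, 5/149 = 3.4% fatigue. Their sum is 20.1%, which may count a patient twice.

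**4. Carry-over.** Let f be the share of Arm 1 starting sorafenib within 30 days and r the share of sorafenib's Grade 3/4 events that arise before the window closes. The documents give neither. Assume f = 10% to 50% and r = 25% to 50%, and that LY2157299 itself causes none of these events.

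Events carried into Arm 1 = 30 x f x r x 0.201. Expected in Arm 3 = 30 x 0.201 = 6.03. Share of the contrast lost = f x r.

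| f | r | Events carried over | Share of contrast |
|---|---|---|---|
| 10% | 25% | 3 x 0.201 x 0.25 = 0.15 | 2.5% |
| 10% | 50% | 3 x 0.201 x 0.50 = 0.30 | 5% |
| 50% | 25% | 15 x 0.201 x 0.25 = 0.75 | 12.5% |
| 50% | 50% | 15 x 0.201 x 0.50 = 1.5 | 25% |

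**5. One event type, free of double counting.** For Grade 3/4 hand-foot skin reaction, the Arm 3 minus Arm 1 difference is (16/149) x (1 - f x r). It falls from 10.7 points to 10.5 (f x r = 2.5%) or 8.1 (f x r = 25%).

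**6. Effect on the planned test.** With 30 against 30 patients, Fisher's two-sided 5% test has only about 10% power for Grade 3/4 hand-foot skin reaction even without carry-over, so the harm there is to the estimate. For a commoner event, assume a 30% any-grade rate under sorafenib and r = 50%. Arm 1 then carries 1.5% (f = 10%) or 7.5% (f = 50%), and power falls from 92% to 83% or 49%.

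**The case against.** The strongest reply is that the plan already separates causality. The main TEAE and maximum-grade tables have a version limited to related events. Protocol 10.3.1 tells investigators to consider other concomitant treatment as a cause, and the open label in Arm 1 makes that easier. Adverse events are listed by onset date and later therapies by drug and start date, so a reader could match them. This stands in part. However, an investigator's 'does not know' counts as related (Protocol 10.3.1), as does missing causality after dosing (SAP 6.12.2). The all-causality and SAE tables get no relief, and listings give no by-arm rate.

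A second reply is that a 30-day window guards against missing late drug effects, and Protocol 10.3.1.1 collects SAEs for 30 days whatever their cause. This stands. If switching is concentrated in Arm 1, a cut window would shorten observation mainly there and could drop late LY2157299 events. That matters because the cardiovascular lesions in rats were only partly reversible (Protocol 5.1.4). A reader might infer that the cut window should replace the full one; the documents do not support that.

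A reader might also infer that only Arm 1 is affected and that its patients will receive sorafenib. The documents name no next treatment. Section 10.1 collects new therapy dates without distinguishing arms, and unapproved or investigational drugs after Arms 2 and 3 would fall in the same window. Sorafenib after Arm 1 is a reasonable inference from its standing as first-line care, no more.

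**Conclusion.** The gap in the definition is real. Neither document ends the treatment-emergent window at the next anticancer therapy, although a switch inside it is foreseen and dated. The all-causality TEAE, maximum-grade and SAE tables can therefore carry post-study sorafenib toxicity, probably mainly into Arm 1, and understate its difference from the sorafenib control.

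The size cannot be fixed from the documents. Under the assumed ranges it is about 0.15 to 1.5 Grade 3/4 events in 30 patients, or 2.5% to 25% of the contrast. A reader might take the upper end as the expected loss, but it requires half of Arm 1 to switch within 30 days and half of the events to appear in that time. Patients who switch late in the window contribute less.

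Nor is safety the only reason for Arm 1. Section 8.2 also seeks efficacy information on monotherapy, and Section 6.2 lists its survival hazard ratio as a secondary objective. Primary overall survival and the sample size are not affected.

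**What to change.** Keep the full 30-day TEAE, SAE and 30-day death tables as planned. Add to SAP 6.12.2 prespecified by-arm, all-causality TEAE, maximum-grade and SAE tables that end at the earlier of 30 days after discontinuation and the day before the first post-discontinuation systemic anticancer therapy. State that the Arm 1 versus Arm 3 safety comparison is to be interpreted from the cut and full tables side by side. List separately the adverse events that start on or after the new therapy, naming the drug.

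The cost is a little programming, since the therapy start date is already collected. The downside is that late LY2157299 events after a switch appear only in the full-window tables and the listing, which is why the full tables must stay.

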**Table JBAS.9.4. Suggested Sorafenib Dose Modifications for Skin Toxicity**

Skin Toxicity Grade	Occurrence	Suggested Dose Modifications
Grade 1: Numbness, dysesthesia, paresthesia, tingling, painless swelling, erythema or discomfort of the hands or feet that does not disrupt the patient's normal activities	Any occurrence	Continue treatment with sorafenib and consider topical therapy for symptomatic relief
Grade 2: Painful erythema and swelling of the hands or feet and/or discomfort affecting the patient's normal activities	1st occurrence	Continue treatment with sorafenib and consider topical therapy for symptomatic relief. If no improvement within 7 days, see below
	No improvement within 7 days or 2nd or 3rd occurrence	Interrupt sorafenib treatment until toxicity resolves to Grade 0-1. When resuming treatment, decrease sorafenib dose by 1 dosage level (400 mg daily or 400 mg every other day)
	4th occurrence	Discontinue sorafenib treatment
Grade 3: Moist desquamation, ulceration, blistering or severe pain of the hands or feet, or severe discomfort that causes the patient to be unable to work or perform activities of daily living	1st or 2nd occurrence	Interrupt sorafenib treatment until toxicity resolves to Grades 0-1. When resuming treatment, decrease sorafenib dose by 1 dosage level (400 mg daily or 400 mg every other day)
	3rd occurrence	Discontinue sorafenib treatment

Source: Nexavar (sorafenib) package insert

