6.16. Clinical Trial Registry Analyses

Additional analyses will be performed for the purpose of fulfilling the Clinical Trial Registry (CTR) requirements.

Analyses provided for the CTR requirements include the following:

Summary of adverse events, provided as a dataset which will be converted to an XML file. Both Serious Adverse Events and ‘Other’ Adverse Events are summarized: by treatment group, by MedDRA Preferred Term.

- An adverse event is considered ‘Serious’ whether or not it is a treatment emergent adverse event (TEAE).
- An adverse event is considered in the ‘Other’ category if it is both a TEAE and is not serious. For each Serious AE and ‘Other’ AE, for each term and treatment group, the following are provided:
 - the number of participants at risk of an event
 - the number of participants who experienced each event term
 - the number of events experienced.
- Consistent with www.ClinicalTrials.gov requirements, ‘Other’ AEs that occur in fewer than 5% of patients/subjects in every treatment group may not be included if a 5% threshold is chosen (5% is the minimum threshold).
- AE reporting is consistent with other document disclosures for example, the CSR, manuscripts, and so forth.

7. References

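### The related row of the SAP's AE overview is worded as a count of AEs, not patients, so one re-graded toxicity can count several times and the row cannot be compared across arms

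*SAP*

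**What the plan says.** SAP 6.12.2 introduces the table as "An overview of AEs including the number and percentage of patients with" at least one TEAE, at least one Grade 3/4 event, at least one SAE, discontinuation due to an AE or to an SAE, and death due to an AE on treatment or within 30 days of discontinuation. That makes seven categories, all counted in patients. It then adds: "Additionally, the number of AEs related to study treatment in each of the previous categories will be given".

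Three other rules in 6.12.2 bear on what such a count would contain:

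- **Record rule.** If an AE has not resolved but its severity or seriousness changes, "then the date of the change is entered as the end date and a new AE record is generated". The new record starts on the date the old one ends.
- **TEAE rule.** "If the post-dose LLT is not present as a pre-dose term, then the AE is a TEAE". For a term that was present before dosing, a post-dose record qualifies only if its severity exceeds the worst pre-dose grade.
- **Count-once rule.** The section states that "a patient with multiple adverse events within a SOC or PT is only counted once towards the total of this SOC or PT".

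SAP 6.16 (Clinical Trial Registry Analyses) asks, for each term and group, for participants at risk, participants affected and "the number of events experienced".

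Protocol 12.2.11 plans an overall summary of possibly related AEs, repeated regardless of causality, with incidence rates compared between arms by Fisher's exact test.

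**The concern.** The overview changes unit part-way through: patients for all causes, AEs for related events. The two sets of rows cannot be set against each other, and no percentage can be formed from the related row.

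The unit it changes to is not a clinical episode either. Under the record rule, an AE in the database is a period at one grade and one seriousness status, and improvement splits a record just as worsening does. The count then depends on how often a toxicity was re-graded as well as on how many patients had it.

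The stake is the descriptive safety comparison. Protocol 8.2 gives the purpose of the monotherapy arm as a safety comparison of LY2157299 with sorafenib, and related events bear directly on that. The primary overall survival analysis is not touched.

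**Working it through.** The plan states no figure here to reproduce. The check applies the SAP's own rules to example grade paths, then tests how arm comparisons respond.

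**1. Records per episode.** An unresolved episode with k changes of grade gives k + 1 records. For a related term absent before dosing, every record meets the TEAE rule, including those at a lower grade.

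| Grade path, one patient | k | Records (related TEAEs) | Grade 3 records | Patients |
|---|---|---|---|---|
| 2 | 0 | 1 | 0 | 1 |
| 1-2-1 | 2 | 3 | 0 | 1 |
| 1-2-3-2-1 | 4 | 5 | 1 | 1 |
| 2-3-2-3-2 | 4 | 5 | 2 | 1 |

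**2. Does another rule prevent this?** The count-once rule names SOC and PT totals. The overview categories are neither. No rule in 6.12.2 or 6.16 joins the records of one continuing episode.

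**3. Which categories are exposed?** TEAE, Grade 3/4 and SAE: three of the seven. SAE records multiply only if successive records of an episode are each flagged serious, which the documents leave open. A death cannot repeat within a patient, and a treatment discontinuation hardly can.

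**4. Arm sensitivity.** Inputs: planned arms of 30 monotherapy, 60 combination and 30 control (SAP 5.2). Two assumptions, because the documents give neither figure: 50% of patients affected in every arm, and 1 to 3 records per affected patient. Count = arm size × 0.5 × records per affected patient.

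| Records per affected patient (monotherapy / sorafenib arms) | Monotherapy | Combination | Control | Control ÷ monotherapy | Combination ÷ monotherapy |
|---|---|---|---|---|---|
| 1 / 1 | 15 | 30 | 15 | 1.0 | 2.0 |
| 2 / 2 | 30 | 60 | 30 | 1.0 | 2.0 |
| 3 / 3 | 45 | 90 | 45 | 1.0 | 2.0 |
| 2 / 3 | 30 | 90 | 45 | 1.5 | 3.0 |
| 3 / 2 | 45 | 60 | 30 | 0.67 | 1.33 |
| 1 / 3 | 15 | 90 | 45 | 3.0 | 6.0 |
| 3 / 1 | 45 | 30 | 15 | 0.33 | 0.67 |

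Incidence is 50% in every arm in every line. Counted as patients, the row would read 15/30, 30/60 and 15/30 throughout. Two effects separate:

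- The factor of 2.0 for the combination arm comes from the 1:2:1 allocation alone.
- The control-to-monotherapy ratio can fall either side of 1, depending wholly on the assumed records per patient.

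**5. Match with the protocol.** Fisher's exact test needs patients with and without an event in each arm. A count of records supplies neither.

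**6. Is the information available elsewhere?** 6.12.2 lists related and all-causality versions of the patient-level tables for TEAEs, serious TEAEs leading to discontinuation, maximum grade and grade group. The SAE table carries no such split. As listed, the overview is therefore the only summary table in that section that separates all related SAEs.

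**The case against.** **The sentence may be loose wording.** The categories it refers back to are patient categories, and Protocol 12.2.11 treats the related and all-causality summaries alike. Patients may well be what was meant. This stands as a reading of intent, but a programmer following the text would count records, so the wording needs correcting either way.

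**Most of the safety comparison is protected.** Related TEAEs appear as number and percentage of patients by SOC, PT and maximum grade, and re-grading cannot inflate those tables. The registry output gives participants affected beside events. Both points stand, and they confine the problem to one descriptive row and one column.

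**Not every record counts.** For a term present before dosing, records no worse than the pre-dose maximum drop out of the TEAE category. This also stands and narrows the effect for such terms.

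**A stronger reading is tempting:** that the sorafenib arms will look worse than monotherapy. For certain skin toxicities Protocol Table JBAS.9.4 says "Interrupt sorafenib treatment until toxicity resolves to Grade 0-1", which makes repeated grade changes plausible. The documents do not carry the inference further:

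- The same table continues sorafenib for Grade 1 and for a first Grade 2 occurrence.
- A toxicity that resolves fully and recurs is a new event, not a split record.
- Protocol 9.4.1.1 has its own rule omitting LY2157299 until listed toxicities resolve, and the 14-days-on, 14-days-off schedule could itself make grades fluctuate.
- The study-period visit schedule is common to all arms.
- No re-grading frequency is given for any arm.

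**Conclusion.** The point holds as a mismatch of units with a real counting consequence. Followed as written, the related row counts one fluctuating toxicity several times in the TEAE, Grade 3/4 and SAE categories, and gives raw counts that cannot be compared across 1:2:1 arms.

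The allocation effect is certain in size: a factor of 2 for the combination arm at equal toxicity per patient and equal records per affected patient. The re-grading effect is not. Its size rests on the assumed 1 to 3 records per affected patient, and its direction between sorafenib and monotherapy is unknown, so no claim that either looks worse is warranted.

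The correction is worth making although the row is descriptive, because the related SAE split is listed nowhere else among the 6.12.2 summary tables and the protocol's incidence comparison cannot be made from it.

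**What to change.** - **SAP 6.12.2.** Reword the sentence so that the related row gives the number and percentage of patients with at least one related AE in each category, in the same unit as the other rows.
- **Anywhere events are counted, including SAP 6.16.** First merge contiguous records of the same patient and LLT, where one record's end date equals the next one's start date, into one event at its maximum grade. State how seriousness and relatedness are set when the merged records differ, and label the column as episodes.

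The cost is one sentence and a short derivation. The dates needed are already collected under the record rule, so no new data are required.
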